### **9.3.2 Time to Withdrawal for Any Reason**

Time to Withdrawal for Any Reason is defined as the duration from start of treatment to study withdrawal for any reason. If the subject does not discontinue from the study, time to withdrawal for any reason will be censored at the date of study completion; this is expected to be the Day 42 (+ 2 days) Follow-up Telephone Call.

Time to Withdrawal for Any Reason (days) = (Date of study withdrawal – Date of first dose) + 1

Time to Withdrawal for Any Reason will be analyzed as described above for the time to first AE.

If a subject does not discontinue or withdraw from the study, the time to discontinuation will be censored at the date of study completion.

### **9.3.3 Adverse Event Summaries**

An adverse event (AEs) will include any newly occurring event or previous condition that has increased in severity or frequency since administration of the first dose of study drug. If there are partial AE start date and times, an AE will be date/time of onset on or after the time of first dose of study medication on Day 1 to Day 42 (+2 day) Follow-up Telephone Call.

Adverse events will be coded by preferred term (PT) and system organ class (SOC) using MedDRA (version to be delineated in the CSR).

Each AE will be graded for severity and classified into one of five categories according to Division of AIDS (DAIDS) Table for Grading the Severity of Adult and Pediatric AEs (protocol Appendix 4): Grade 1 (mild), Grade 2 (moderate), Grade 3 (severe), Grade 4 (life threatening), and Grade 5 (death).

Each AE is assessed for relationship to study drug. Terms to describe the degree of causality between a study drug and an event are definitely, probably, possibly, unlikely related or not related. If relationship to study drug is missing, it will be regarded as definitely related for the purposes of data summaries.

Frequency of AEs will be calculated for each system organ class, by preferred term and treatment group for the number of subjects reporting the event for the Safety Population and the Per-Protocol Safety Population.

Each AE will be counted only once per subject at the preferred term level.

For summaries of AEs by system organ class, preferred term, maximum severity and treatment the rule is as follows: if a subject experiences more than one episode of an AE, the subject is counted only once by the maximum severity of the episode (preferred term). If a subject has more than one AE within a system organ class, the subject is counted only once in that system organ class. Similarly, when study drug relationship is presented, the strongest relationship to study drug is used for AEs mapping to the same preferred term, or within a system organ class.

Summaries will be ordered by descending frequency of SOC and then, within a SOC, by overall descending frequency of PT for the TPOXX group.

The following AE tables will be produced:

- An Overall summary of the number of events and number and percentage of subjects reporting the following:
  - All AEs
  - Serious AEs
  - Treatment-related AEs
  - AEs leading to early study discontinuation and
  - AEs leading to death
- AEs overall by system organ class and preferred term
- AEs by maximum severity, overall and by system organ class and preferred term
- AEs by maximum relationship to study treatment, overall and by system organ class and preferred term
- Treatment-related AEs, overall and by system organ class and preferred term
- Serious AEs, overall and by system organ class and preferred term.

In general, all AE tables will show the number and percentage of subjects with an event. The number of events overall by treatment group and dosing regimen will also be included.

A listing of all AEs will provide details including system organ class, preferred term, verbatim term, whether treatment was emergent or not, severity, relationship to treatment, onset and resolution date and time, duration (in days for any AEs lasting longer than 24 hours, in hours otherwise, derived as stop date and time – start date and time), action and outcome. Similar listings will be presented for SAEs, AEs with Grade 3 or higher, AEs with a fatal outcome (or Grade 5) and AEs leading to early withdrawal.

Toxicity grades for laboratory tests will be determined according to the [DAIDS AE Grading Table](#). The maximum post-baseline grade increase from baseline grade will be summarized by treatment group and dosing regimen and overall for the safety population and PP safety population using frequency and percentage of subjects with increase to grade 1, 2, 3, 4, 1 to 4, 2 to 4, and 3 to 4, respectively.

All AEs will be presented in a data listing.

#### **9.4. Clinical Laboratory Evaluations**

The following laboratory tests will be performed:

Hematology	Hematocrit, hemoglobin, mean corpuscular hemoglobin, mean corpuscular hemoglobin concentration, total and differential leukocyte count (basophils, eosinophils, lymphocytes, monocytes, neutrophils), mean corpuscular volume, platelet count, red blood cell count, and red cell distribution width.
Serum Chemistry	Alanine aminotransferase, albumin, alkaline phosphatase, anion gap, aspartate aminotransferase, bilirubin (total), blood urea nitrogen, calcium, carbon dioxide, chloride, creatinine, creatinine clearance (calculated (a) ), gamma-glutamyltransferase, globulin, glucose, lactate dehydrogenase, phosphorus, potassium, sodium, total protein, and uric acid
Urinalysis	Appearance, bilirubin, blood, color, glucose, ketones, leukocyte esterase, microscopy (performed if dipstick is $\geq 1+$ ; includes bacteria, casts, crystals, epithelial cells, red blood cells, and white blood cells), nitrites, pH, protein, specific gravity, and urobilinogen.

(a) Creatinine clearance will be calculated using the Cockcroft-Gault formula:

$$\text{Creatinine clearance (mLmin /)} = \frac{[140 - \text{age(years)}] \times \text{weight(kg)}}{72 \times \text{serum creatine } \left( \frac{\text{mg}}{\text{dL}} \right)} \{ \times 0.85 \text{ if female} \}$$

The hematology, serum chemistry, and urinalysis tests will be performed at the time points indicated in the schedule of assessments (schedules of assessments can be found in [Section 13](#)).

Glycosylated hemoglobin and a fasting lipid panel including cholesterol (total, high-density lipoprotein, calculated low-density lipoprotein, and triglycerides) will be performed at screening.

For women of childbearing potential, serum pregnancy test will be performed at the screening visit and analysed by PPD Central Lab. A urine pregnancy test will be performed and read locally at check-in on Day -1 (PK subset) or predose on Day 1 (Non-PK subset). Serum pregnancy tests will be read by PPD Central Lab at the time points indicated in the schedules of events ([Section 13](#)). All positive urine pregnancy tests will be verified using the  $\beta$ -human chorionic gonadotropin test.

For postmenopausal women, a serum follicle-stimulating hormone test will be performed at screening.

All clinical laboratory test results will be presented in the data listings. Laboratory values that are outside of the normal reference range will be flagged in the data listings.

Actual results and change from baseline for hematology, serum chemistry and urinalysis at each time point will be summarized for the Safety and PP Safety Populations by treatment group and dosing regimen at each time point using descriptive statistics. Shift from baseline in terms of low/normal/high for hematology and serum chemistry tests, and in terms of normal/abnormal for urinalysis tests will be summarized for the safety population.

A urine drug screen for alcohol, cotinine, amphetamines (including methamphetamines and ecstasy/methylenedioxymethamphetamine), barbiturates, benzodiazepines, cannabinoids

(including tetrahydrocannabinol), cocaine metabolites, and opiates (including heroin, codeine, and oxycodone) will be performed at screening and sent to the central lab.

Day –1 (Check-in - PK Subset or Day 1 (Predose - Non-PK Subset) ([Section 13](#)):

A urine drug screen for cotinine, amphetamines (including methamphetamine and ecstasy/methylenedioxymethamphetamine), barbiturates, benzodiazepines, cannabinoids (including tetrahydrocannabinol), cocaine metabolites, and opiates (including heroin, codeine, and oxycodone) will be performed and read locally. Blood alcohol will be tested using a breathalyzer device at the clinical investigative site.

Abnormal clinical laboratory values will be flagged as either high or low (or normal or abnormal) based on the reference range for each laboratory parameter. The investigator will determine whether any of the abnormally high or low results are clinically significant or not clinically significant.

Toxicity grades for laboratory tests will be determined according to the DAIDS AE Grading Table.

Actual values and changes from baseline for clinical laboratory test results, will be summarized for Safety and PP Safety Populations and by treatment group and dosing regimen at each time point using descriptive statistics.

## **9.5. Vital Sign Measurements**

Vital signs will be measured after the subject has been seated for at least 5 minutes at the time points indicated in the schedule of events ([Section 13](#)).

Vital sign measurements will include systolic and diastolic blood pressures, heart rate, respiratory rate, and body temperature.

The investigator will determine whether any of the vital sign measurements are clinically significant or not clinically significant. Clinical significance is defined as any variation in results that has medical relevance and may result in an alteration in medical care (e.g., active observation, diagnostic measures, or therapeutic measures). If a clinically significant change from the screening values is noted, the clinically significant value and reason for clinical significance will be documented on the AE page of the subject's eCRF. The investigator will continue to monitor the subject with additional assessments until the value has reached the reference range or the value at screening or until the investigator determines that follow up is no longer medically necessary.

Summary tables presenting observed values and changes from baseline will be summarized for Safety and PP Safety populations and by treatment group and dosing regimen at each time point using descriptive statistics.

All vital sign data will be presented in a data listing. All vital signs, body weight, and height measurements will be presented in a data listing.

## **9.6. Physical Examination**

Full physical examinations will be performed at the time points indicated in the schedules of events ([Section 13](#)) and will include, at minimum, assessment of the following body systems: head, ears,

eyes, nose, and throat; cardiac (including auscultation of heart); pulmonary (chest) auscultation of lungs; abdomen; skin; musculoskeletal system; lymphatic system; and neurologic system (cranial nerves, sensation, motor function, coordination, reflexes, and mental status).

A symptom-directed physical examination will be performed on Day 31 (PK subset only) as well as unscheduled physical examinations at the discretion of the investigator, if necessary, to evaluate AEs or clinical laboratory abnormalities.

Height and weight will be measured at screening only.

Physical examination results will be presented in a data listing.

### **9.7. Electrocardiograms**

A standard 12-lead ECG will be obtained after the subject has been in the supine position for at least 10 minutes at the time points indicated in the schedule of events ([Section 13](#)).

Electrocardiogram assessments will include comments on whether the tracings are normal, abnormal, indeterminate, not evaluable and unknown. The following parameters will be measured and reported: heart rate; PR interval, QT intervals; QT interval corrected using Fridericia's formula; QRS duration and RR interval. All ECGs must be performed by an experienced ECG technician.

The investigator will determine whether any of the 12-lead ECG results are clinically significant or not clinically significant. Clinical significance is defined as any variation in results that has medical relevance and may result in an alteration in medical care (e.g., active observation, diagnostic measures, or therapeutic measures). If a clinically significant change from screening is noted, the clinically significant value and reason for clinical significance will be documented on the AE page of the subject's eCRF. The investigator will continue to monitor the subject with additional assessments until either the values have reached reference range or the values at screening or until the investigator determines that follow-up is no longer medically necessary.

Summaries will be presented separately for the Safety Population and the PP Safety Population and will also be presented by treatment and dosing regimen. ECG tables presenting observed values and changes from baseline will be presented for numeric results. Changes from baseline to each scheduled post baseline visit will be presented.

All ECG data will be presented in a data listing.

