  - Aspartate aminotransferase >2 times above the upper laboratory reference range
  - Alkaline phosphatase >20% above the upper laboratory reference range
  - Hemoglobin A1c ≥7.0%
  - Cholesterol ≥300 mg/dL and low-density lipoprotein ≥190 mg/dL
27. Subject has hypertension that is poorly controlled (repeat reading >140 mm Hg systolic and/or >90 mm Hg diastolic) or blood pressure considered to be clinically significant by the investigator. Blood pressure may be retested twice in the sitting position at 5-minute intervals.
28. Subject has a resting heart rate of <40 beats per minute or >110 beats per minute at screening.
29. Subject has an abnormal ECG at screening that is determined by the investigator to be clinically significant.
30. Male subject has a QT interval corrected using Fridericia's formula (QTcF) >450 ms or female subject has a QTcF >470 ms at screening or Day 1 or Day -1 (PK subset).
31. Subject has used any prescription antiviral drugs with the intention of coronavirus disease (COVID-19) treatment or prophylaxis, including those that are thought to be effective for prevention of COVID-19 but have or have not been licensed for this indication, within 1 month prior to study entry or during the study.
32. In the opinion of the investigator, the subject is not suitable for entry into the study.
33. Subject is a member or family member of the investigator or study site personnel.
34. Subject has previously participated in this clinical trial.

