Time from the first dose to the first AE or to discontinuation from study for any reason will be analyzed using Kaplan-Meier quartile estimates along with 2-sided 95% CIs. Treatment groups will be compared using the log rank test stratified by age group and site. If a subject does not experience any AE or does not discontinue from study, the time to first AE or time to discontinuation will be censored at the date of study completion.

Toxicity grades for laboratory tests will be determined according to the DAIDS AE Grading Table. The maximum postbaseline grade increase from baseline grade will be summarized by treatment group and BID and TID study drug dosing regimen and overall for the Safety Population and PP Safety Population using frequency and percentage of subjects with increase to grade 1, 2, 3, 4, 1 to 4, 2 to 4, and 3 to 4, respectively.

Actual values and changes from baseline for clinical laboratory test results, vital sign measurements, and 12-lead ECG results will be summarized by treatment group and BID and TID study drug dosing regimen at each time point using descriptive statistics (number of subjects, mean, SD, median, minimum, and maximum). Shift tables will be generated for clinical laboratory test results. Physical examination findings will be presented in a data listing.

Narratives will be presented for all deaths, subjects who reported SAEs, subjects withdrawn because of AEs, and grade 3 AEs deemed by the investigator to be possibly, probably, or definitely related to study drug.

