### **4. General Statistical Considerations**

All statistical analyses will be conducted using statistical analysis system SAS® Version 9.4 or higher (SAS Institute, Cary, NC).

Descriptive statistics for continuous variables will include number of subjects, mean, standard deviation (SD), median, minimum, and maximum, unless otherwise noted. For categorical variables, frequencies and percentages will be presented.

All tables, listings, and figures will be presented by treatment and weight. The treatments below will be used for presentations:

- TPOXX 600mg
- Matching TPOXX Placebo

Unless otherwise indicated, outputs which are summarized by treatment and weight will be summarized for each dose level for subjects on active study drug.

All data listings will be sorted by treatment (TPOXX or placebo), by treatment regimen (BID or TID dosing), and subject number.

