## **Subgroups**

The effects of age group (18 to 30 years, 31 to 45 years, 46 to 64 years, and 65 to 80 years) used for stratification at randomization and site will be investigated for AE and severe AE rates. Time to first AE or severe AE and time to withdrawal for any reason will be calculated.

Study day is relative to first dose of study drug. Study days are calculated with respect to the first dose date as below:

- If the assessment/observation date is on or after the first dose date, then Study Day = Assessment/Observation Date – First Dose Date + 1;
- Otherwise, Study Day = Assessment/Observation Date – First Dose Date.

Baseline will be defined as the last non-missing assessment (including repeated and unscheduled assessments) before the first dose of study drug administration, unless otherwise specified.

For summary of safety assessments, if there are repeated measurements at a time point, the first non-missing assessment at that time point will be used in the summary tables.

Unscheduled results will not be included in the summary tables, except for determining Baseline, but will be presented in data listings.

The methodology and data handling specifications for PK data are detailed in [Section 8](#).

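### ECG results get per-visit descriptive statistics and a listing, but no table counts subjects by arm over a QTcF limit, and the SAP table index has no ECG table

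*Combined protocol and SAP*

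**What the plan says.** The ECG plan has four parts.

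- **Tables.** SAP 9.7: "ECG tables presenting observed values and changes from baseline will be presented for numeric results", by treatment and regimen, for the Safety and PP Safety Populations. Protocol 7.3.2 agrees: "vital sign measurements, and 12-lead ECG results will be summarized by treatment group and BID and TID study drug dosing regimen", "using descriptive statistics (number of subjects, mean, SD, median, minimum, and maximum". SAP section 4 sets the same default: "Descriptive statistics for continuous variables will include number of subjects, mean, standard deviation (SD), median, minimum, and maximum, unless otherwise noted".
- **Listing.** SAP 9.7: "All ECG data will be presented in a data listing".
- **AE route.** If the investigator judges a change from screening clinically significant, "the clinically significant value and reason for clinical significance will be documented on the AE page of the subject's eCRF" (SAP 9.7).
- **Which tracings enter the tables.** SAP section 4, under Subgroups: "Unscheduled results will not be included in the summary tables, except for determining Baseline, but will be presented in data listings". The same paragraphs take the first non-missing value when a measurement is repeated at a time point.

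The documents also contain QTc limits, used for other purposes. Exclusion criterion 30 reads "Male subject has a QT interval corrected using Fridericia's formula (QTcF) >450 ms or female subject has a QTcF >470 ms at screening" and applies again at Day 1 or Day -1. The QTc row of the DAIDS table (protocol Appendix 4) sets Grade 3 at more than 0.50 s or at least 0.06 s above baseline, with Bazett's correction according to its footnote.

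**The concern.** A QT effect may appear as large rises in a few subjects rather than a shift in everyone. Per-visit descriptive statistics are poorly suited to that pattern: the mean dilutes it, and the maximum reports one value without saying how many subjects lie near it. The documents treat QTc as a threshold measure at entry and in AE grading, yet no planned output reports how many subjects in each arm cross a threshold on treatment. Safety is the primary objective, and ECG is a named component of the primary outcome measure (SAP 4.5.1). At stake is whether the report can give a prespecified QTcF prolongation rate by arm, or must leave readers to build one from a listing after unblinding.

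**Working it through.** **1. The plan's own figure.** SAP 4.2 gives about a 95% chance of seeing at least one event of 1% incidence in 300 TPOXX subjects. Check: 1 − 0.99^300 = 0.951, which reproduces it. The sample size is thus explained by the ability to observe uncommon events. No ECG-specific figure is stated.

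**2. Is a count planned anywhere?**

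| Place | Coverage |
|---|---|
| SAP 9.7, protocol 7.3.2 | Per-visit values and changes; no categories |
| SAP 9.3.3, grade increase from baseline | Laboratory tests only |
| SAP 9.4, shift tables | Laboratory tests only |
| SAP section 14, table index | Laboratory and vital-sign change tables; no ECG table |
| SAP section 15, listing index | ECG as Listing 16.2.9.2 |

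No count is planned, and the index omits even the tables that 9.7 promises.

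**3. What the maximum can show.** Each cell (treatment, regimen, visit) yields one maximum. Protocol Table 9-2 schedules five post-dose ECGs for non-PK subjects (Day 1 post-dose, Days 7, 14, 21 and 29). Five maxima could come from one subject or five, and the table cannot tell which. A symptom-triggered unscheduled ECG, or a repeat longer than the first tracing, does not enter at all.

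**4. Illustration.** Arm sizes of 356 and 89 come from SAP section 3. The following are assumptions, not document figures: 7 TPOXX subjects with a 60 ms rise at a given visit, no change in anyone else's average, and an SD of change of 10 to 20 ms.

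- Shift in the TPOXX mean: 7 × 60 / 356 = 1.2 ms.
- SE of the difference in means: SD × √(1/356 + 1/89) = 1.19 ms at SD 10 and 2.37 ms at SD 20.
- 95% half-width: 1.96 × SE = 2.3 to 4.7 ms, so the shift lies inside ordinary sampling noise.
- As a count: 7/356 = 2.0%, Clopper-Pearson 95% CI 0.8 to 4.0%. Placebo 0/89: upper limit 1 − 0.025^(1/89) = 4.1%.

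**5. Range.** With a 60 ms rise in 0.5%, 1% or 2% of TPOXX subjects, the expected number affected is 1.8, 3.6 or 7.1, and the mean moves 0.3, 0.6 or 1.2 ms. At 1%, the chance of at least one such subject among 356 is 97%, and of at least two 87%. The maximum would therefore usually reveal that an outlier exists, but usually more than one subject would be affected and the number would go unreported.

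**The case against.** The strongest reply is that the plan is fuller than a table of means. Maxima of the changes are specified, so a 60 ms rise at a scheduled visit should appear in a maximum cell. Every ECG is listed, so a count can be made afterwards. Clinically significant changes become AEs, tabulated by preferred term, severity and arm (SAP 9.3.3). Grade 3 ECG results go to the medical monitor (protocol 4.4.3), and the DSMB receives an ECG summary (protocol 9.3.3.1.4). No QT endpoint is stated, and the 450/470 ms limits are eligibility rules.

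Most of this stands, and it rules out two stronger readings that a reader might infer. One is that ECG safety rests on means alone, so outliers cannot appear; the specified maximum, the listing and the AE tables contradict that. The other is that the trial could never state a QTcF rate; the listing would allow one, though not one prespecified.

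These routes still do not replace a count. A listing has no denominator, interval or prespecified category. The AE route depends on investigator judgement, and its QTc grades use Bazett while the trial reports QTcF. The maximum has the limits shown in the working.

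It would also be wrong to say that a test of means would lack power, since the ECG analysis is descriptive and no such test is planned. Nor is the count a strong comparison: 7/356 against 0/89 gives a two-sided Fisher p of 0.35.

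**Conclusion.** The gap is real but limited. ECG results are described by visit and listed; no table gives the number of subjects by arm whose QTcF exceeds a value or change limit after dosing, and the section 14 index contradicts 9.7 by containing no ECG table. These points rest on the text alone. The size is illustrative: in the assumed example, a 2.0% rate of 60 ms rises would appear as a 1.2 ms movement in the mean, and per-visit maxima would not show how many subjects were affected. The example depends on the assumed incidence, rise and SD. The documents do not support reading this as evidence of a QT problem with TPOXX, or as a claim that the added table would settle a between-arm difference. It would give a rate with an interval in each arm, from data already collected. That suits a safety trial sized around 1% events and is worth doing before unblinding.

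**What to change.** Add to SAP 9.7 and to the section 14 index a table for the Safety and PP Safety Populations, by treatment and regimen. It should give the number and percentage of subjects, with Clopper-Pearson intervals, whose worst post-baseline QTcF:

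- is above 450 ms (men) or above 470 ms (women);
- is above 500 ms;
- is at least 60 ms above baseline.

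These are reporting categories only. The first comes from exclusion criterion 30; the other two come from the DAIDS QTc row, applied here to QTcF. They imply no change to eligibility, withdrawal or halting.

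State that the table includes unscheduled and repeat ECGs, as an explicit exception to the SAP section 4 rule. Add to the index the per-visit ECG summary tables that 9.7 already promises, for both populations.

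The cost is a small amount of programming; no new data and no protocol amendment are needed. The drawback is that single tracings, with the worst of several taken, will produce some chance outliers in both arms, so the table should be labelled descriptive and read against placebo.
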